GnRHAG, **SA3**) in combination with the use of ^{11}C -acetate PET methodologies.

IV. Research Methods

A. Outcome Measure(s): *The primary study outcome is BAT oxidative metabolism (^{11}C -acetate clearance rate) during basal and cold-stimulated conditions. Secondary outcomes are BAT activity volume (^{18}FDG uptake) during basal and cold-stimulated conditions; CIT; ^{18}FDG update into muscle; shivering (sEMG & ^{18}FDG uptake in deep skeletal muscles); and changes in skin and core temperature during cold exposure. Serum concentrations of hormones and metabolites will be measured primarily as descriptive variables, but we will also explore the association of these measures with the primary study outcomes.*

B. Description of Population to be Enrolled: Premenopausal volunteers will be healthy, eumenorrheic women, aged 18-50 yrs. Eumenorrheic status will be verified by regular menses (no missed cycles in previous year; cycle length 25-35 d). Postmenopausal volunteers will be healthy women who have no menses for at least 12 months; postmenopausal status will be confirmed based on FSH (≥ 50 mIU/ml). The primary **exclusion** criteria are:

- Pre- and Postmenopausal women
 - BMI >40 kg/m 2 ; we have purposely used a wide range of BMI to facilitate recruitment.
 - Thyroid dysfunction, defined as an ultrasensitive thyroid stimulating hormone (TSH) <0.5 or >5.0 mU/L (pre- and postmenopausal women); volunteers with abnormal TSH values will be re-considered for participation in the study after follow-up evaluation by the PCP with initiation or adjustment of thyroid hormone replacement.
 - Uncontrolled hypertension defined as resting systolic BP >150 mmHg or diastolic BP >90 mmHg; participants who do not meet these criteria at first screening will be re-evaluated, including after follow-up evaluation by the PCP with initiation or adjustment of anti-hypertensive medications
 - Self-reported diabetes or fasting glucose >126 mg/dL
 - Use of tobacco products (last 6 months)
 - Selective serotonin reuptake inhibitors (SSRIs) or any other medication or condition that may affect brown fat activity. The decision will be based on the judgement of the study physician and primary investigator.
 - Serious illness within the last 6 months
 - Confirmed positive COVID test within the last 6 months
- Additional exclusion criteria for postmenopausal women
 - Current use of hormonal replacement therapy or use <10 yrs ago.
 - Women who have undergone surgical menopause.

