Screening - After providing informed consent, volunteers will undergo screening procedures, including a review of medical history (including menstrual cycle history), and a clinical laboratory evaluation including fasting glucose, creatinine, liver function tests, thyroid function tests, and a complete blood count. TSH will be measured in the Clinical and Translational Research Center (CTRC) core lab; other chemistries (metabolic panel, CBC) will be performed by the University of Colorado Hospital laboratory. This will be followed by measurement of bone mineral density (BMD). Premenopausal volunteers with a history of fragility fracture or low BMD (lumbar spine or proximal femur z-scores ≤ -2.0) will not be enrolled in the intervention study because of the possibility that BMD will decrease during GnRH_{AG}.

Serum hormones and metabolites - At study entry and at the end of the intervention (on the day of the cold exposure study), fasted blood samples will be obtained for the measurement of estrone (E₁), E₂, progesterone, testosterone, sex hormone binding globulin (SHBG), follicular stimulating hormone (FSH), leptin, cortisol, free fatty acids, glycerol, and thyroid hormones (T₃, T₄). An additional sample will be obtained at the end of the cooling protocol (at minute 120, before the ¹¹C acetate infusion) for measurement of T₃, T₄, TSH, free fatty acids and glycerol. Changes in these parameters will be evaluated for correlation with the changes in the primary outcomes. In rodents, BAT activation improves glucose tolerance.^{76,82} In humans, BAT activity is inversely associated with fasting blood glucose and hemoglobin A1c (HbA1c),⁴⁷ and cold acclimation induces improvements in insulin sensitivity.⁴³ Thus, samples will also be obtained for the measurement of glucose and insulin for the assessment of insulin resistance by the homeostasis model.⁴⁸ Assays will be performed in the Clinical and Translational Research Center (CTRC) core lab. Samples will be stored at -80° C.

Dual-energy X-ray Absorptiometry (DXA) – Body composition and BMD will be measured using a Hologic Discovery DXA instrument (Waltham, MA).

Waist Circumference (WC) – will be measured using a spring-loaded tape measure. Circumference will be measured at baseline, Visit 3-8, and after 6 months of suppression.

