- **Leuprolide acetate** – A subset of premenopausal women will receive GnRH_{AG} (leuprolide acetate) 3.75 mg/mo by intramuscular injection every 4 weeks for 24 weeks (6 doses).
 - Contraindications for use include: hypersensitivity to GnRH, GnRH agonist analogs or any of the excipients in Lupron Depot; undiagnosed vaginal bleeding; known or suspected pregnancy; lactation.
 - In women who are pregnant, use of leuprolide acetate may cause fetal abnormalities.
 - Leuprolide acetate may cause an anaphylactic reaction in volunteers with hypersensitivity to GnRH.
 - Regular menstruation should stop during leuprolide acetate therapy but spotting or breakthrough bleeding may occur. Cessation of menses does not ensure that pregnancy will not occur. Normal menstrual function is usually restored within 2-3 months after therapy is discontinued.
 - Leuprolide acetate may cause symptoms related to hypoestrogenism including hot flashes, headaches, nausea, emotional lability, decreased libido, acne, myalgia, sleep disorders, reduction in breast size, hypertension, and vaginal dryness. Bone loss may occur, although the amount lost over the 24-week intervention should be recovered slowly after discontinuation of leuprolide acetate treatment. There may be a development or worsening of depression and the occurrence of memory disorders
 - In rare cases, leuprolide acetate may cause seizures (post-marketing concern).
 - Leuprolide acetate therapy for 24 weeks may cause an increase in FM (~1.0-1.5 kg), a decrease in fat-free mass (1-1.5 kg), an increase in total, LDL, and HDL cholesterol (5-10%), and an increase in triglycerides (15-20%).
 - Local injection site reactions including induration and abscess may occur.
- **Risk of radiation exposure:** Participants will be exposed to radiation during the PET/CT and DXA scans. During the PET/CT scans, participants are exposed to radiation from the CT and from the radiopharmaceuticals. The primary risk of this level of radiation exposure is to the unborn fetus of pregnant women. All participants will perform one DXA and PET/CT study, and a subset of premenopausal women will perform these tests twice. The estimated radiation exposure during each study visit is listed in the table below

Table 2. Estimated radiation exposure (mSv)

Visit #	C-11	F-18	CT	DXA
0				0.015
1	0.91		0.96	
2	0.91	3.5	0.96	
			2.55	
8				0.015
8	0.91		0.96	
9	0.91	3.5	0.96	
			2.55	

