There is no known way to distinguish the energy expenditure associated with shivering and non-shivering thermogenesis in humans. Thus, we will employ rigorous techniques to measure shivering during cold exposure using both sEMG and ¹⁸FDG uptake into deep muscles. These data will be used to quantify shivering and used to interpret differences and changes in CIT.

Postmenopausal women will likely have higher levels of body fat, and body fat may increase in premenopausal women after GnRH_{AG}. As described above, the cooling suit delivers an identical cold stimulus during each study. Our intent is not to determine the maximal activity of BAT, but rather, determine if differences in BAT activation in response to a constant stimulus is either different between pre- and postmenopausal women (**SA2**), or changes after GnRH_{AG} (**SA3**). To account for differences or changes in body composition, REE will be expressed per kg of fat free mass.

We acknowledge that GnRH_{AG} causes a more abrupt withdrawal of ovarian function (i.e., weeks rather than years) and does not generate the same gonadotropin response of menopause (i.e., low rather than high). However, the GnRH_{AG} model is also a strength because it allows us to control the sex hormone environment in a manner that is not possible when studying the natural menopause transition.

F. Data Analysis Plan:

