Sample size justification and power analyses – Sample size calculations and power analyses were performed using SAS 9.4 (SAS Institute, Inc., Cary, NC). For our estimate of effect size, we refer to our previous study that measured CIT in the follicular and luteal phases (Figure 5).⁸ In that study, CIT was higher during the luteal phase ($2530 \pm 524 \text{ kcal} \cdot \text{d}^{-1}$ vs. $2225 \pm 440 \text{ kcal} \cdot \text{d}^{-1}$). Unfortunately, we did not measure BAT activity. Because there were no differences in shivering in this study, we will assume differences in CIT were due to differences in NST; we also assume that this reflects differences in BAT activity. Using a pooled SD of 484 kcal/d, 32 evaluable participants per group (64 total) will provide 80% power to detect a difference of 305 kcal/d in CIT between pre- and postmenopausal women using a 2-sided t-test and a type I error rate at 0.05. Assuming a dropout rate of 15%, 38 participants per group will need to be enrolled to yield the desired sample size of 64 participants. The primary endpoint is BAT oxidative metabolism (¹¹C clearance rate, expressed per mL of BAT per s⁻¹). In our previous study of 12 men, BAT oxidative metabolism increased during cold exposure from 0.35 ± 0.13 to 0.74 ± 0.19 (mean \pm SEM).⁶ Using a pooled SD of 0.45, we estimate that we will have 80.0% power to detect a difference between groups of 0.32 during thermoneutral conditions. Using a pooled SD of 0.66, we will have 84.7% power to detect a difference between groups of 0.50 during cold exposure. In another study, BAT oxidative metabolism at room temperature was 0.35 in lean men vs. 0.05 in overweight men with T2D.¹⁰ We have also reported that BAT oxidative metabolism increased in lean men from 0.73 to 1.59 following a 4-week cold acclimation.⁷ Thus, we consider this to be a meaningful effect size to examine differences in BAT oxidative metabolism between groups during thermoneutral conditions and during cold exposure. A secondary endpoint is BAT activity volume. In our previous study, BAT activity volume was $57 \pm 16 \text{ ml}$ (mean \pm SE).⁶ Using a pooled SD of 55 ml, the study will have 80.0% power to detect a difference of 39 mL between groups. In another study, we reported that BAT activity volume was 48 vs. 4 ml in young healthy men compared to older men with T2DM.⁵ Thus, we consider this to be a meaningful effect size.

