Analysis strategy - Statistical analyses will be performed using SAS 9.4. Analyses will begin with descriptive plots of individual variables to evaluate distributional characteristics and for quality assurance. The effect of menopausal status on each endpoint will be estimated using a linear regression model. The endpoint will be the response variable and a variable indicating menopausal status will be the explanatory variable (equivalent to a 2-sample t-test). If a variable that is related to the response variable is not balanced between menopausal groups, that variable will be included in the regression model to eliminate the potential of the effect of menopausal status being confounded by that variable. For all multivariable analyses, regression diagnostics will be used to ensure that the group of explanatory variables are not collinear. Secondary analyses will be performed to investigate whether REE is associated with either BAT

oxidative metabolism or BAT activity volume. Exploratory analyses will investigate the changes in BAT oxidative metabolism and BAT volume of activity associated with GnRH_{AG} treatment (Aim 3) Because these aims are exploratory, results will be reported using descriptive statistics, mean change, and 95% confidence intervals (CIs) for the changes in the primary and secondary endpoints.

G. Summarize Knowledge to be Gained:

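### The covariate rule for SA1 and SA2 cannot tell a confounder from a mediator or from the group definition, so estradiol, other ovarian hormones or FSH can enter the model and remove part or all of the menopause effect

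*Combined protocol and SAP*

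**What the plan says.** Section IV.F (Analysis strategy) fits a linear regression with menopausal status as the only explanatory variable. It then adds: "If a variable that is related to the response variable is not balanced between menopausal groups, that variable will be included" in the model. The same sentence gives the purpose, which is to prevent confounding of the status effect. There is no candidate list, no threshold for either condition, and no distinction between causes and consequences of menopause. Regression diagnostics for collinearity are planned, without a cut-off or an action.

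Other sections determine which variables can qualify:

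- **Estradiol.** Section I states the overarching hypothesis that E2 modulates BAT activity. Section IV.D (Serum hormones and metabolites) plans the assay: "fasted blood samples will be obtained for the measurement of estrone (E₁), E₂, progesterone", with FSH and leptin in the same list.
- **FSH.** Section IV.B makes it part of the group definition: "postmenopausal status will be confirmed based on FSH (≥ 50 mIU/ml").
- **Body fat.** Section IV.E expects imbalance: "Postmenopausal women will likely have higher levels of body fat". Section III reports an inverse association between body fatness and cold-induced BAT activity, and also says that loss of E2 causes fat gain. Section IV.D (Potential risks) says leuprolide "may cause an increase in FM (~1.0-1.5 kg").
- **Role of hormones.** Section IV.A calls hormones and metabolites primarily descriptive, with associations to be explored.

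**The concern.** SA1 and SA2 ask whether menopausal state influences BAT oxidative metabolism and activity volume. That is a question about the total effect of menopausal state. If the central hypothesis is true, estradiol differs between the groups and is related to BAT, so it meets both conditions of the rule. With estradiol in the model, the status coefficient describes menopause with its proposed mechanism held fixed. With FSH in the model, it describes menopause with part of its own definition held fixed.

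The better the hypothesis fits the data, the more readily the rule admits the variable that absorbs the effect. A null status coefficient could then be produced by the adjustment. Because entry depends on what the data show, the quantity estimated in the primary analysis is also not fixed beforehand.

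**Working it through.** **1. Inputs from the plan (section IV.F, Sample size justification).** There are 32 evaluable women per group, tested "using a 2-sided t-test and a type I error rate at 0.05". Thermoneutral: "Using a pooled SD of 0.45, we estimate that we will have 80.0% power to detect a difference between groups of 0.32". Cold: difference 0.50, SD 0.66, stated power 84.7%.

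**2. Reproduce the stated power.** The noncentrality is difference / (SD × √(2/32)), with √(2/32) = 0.25 and 62 degrees of freedom.

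- Thermoneutral: 0.32 / (0.45 × 0.25) = 2.844, power 79.96% (stated 80.0%).
- Cold: 0.50 / (0.66 × 0.25) = 3.030, power 84.69% (stated 84.7%).

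Both agree. They apply to the model with status alone.

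**3. Add one covariate.** Let r be the correlation of the covariate with status and m the share of the effect that runs through it. Neither is given in the documents; both are assumptions. The variance inflation factor (VIF) is 1/(1 − r²). The noncentrality becomes [difference × (1 − m) / (SD × 0.25)] × √(1 − r²), with 61 degrees of freedom. The residual SD is held at the planned value.

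Worked case, thermoneutral, r = 0.7 (a group difference of about 1.96 within-group SD):

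- VIF = 1/(1 − 0.49) = 1.96.
- m = 0: 2.844 × √0.51 = 2.031, power 51.6%.
- m = 0.5: 1.016, power 17.0%.

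| r | VIF | Thermoneutral, m = 0 | Thermoneutral, m = 0.5 | Either condition, m = 1 |
|---|---|---|---|---|
| 0.5 | 1.33 | 67.9% | 22.8% | 5.0% |
| 0.7 | 1.96 | 51.6% | 17.0% | 5.0% |
| 0.9 | 5.26 | 23.1% | 9.4% | 5.0% |

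In the cold condition at r = 0.7, power is 56.7% (m = 0) and 18.7% (m = 0.5).

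Holding the residual SD fixed matters little. At r = 0.7 and m = 0.5 the slope is 0.16/1.96 = 0.082 per SD, a within-group correlation of 0.082/0.45 = 0.18. The residual SD is then 0.45 × √(1 − 0.18²) = 0.44, and power is 17.4% instead of 17.0%.

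**4. How often would the rule admit such a variable?** The plan gives no threshold, so p < 0.05 was assumed for both conditions. The simulation used 6,000 runs per setting, a true total effect of 0.32 and group imbalances of 1 to 3 SD.

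| Share mediated | Covariate entered | Mean status estimate | Power under the rule |
|---|---|---|---|
| All | 93–98% | about 0.00–0.01 | 5–6% |
| Half | 82–95% | about 0.16 | 16–27% |
| None | 22–63% | 0.28–0.30 | 40–74% |

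**5. Age.** Age is not a consequence of menopause, so it would still qualify under a narrowed rule. At an assumed age gap of 2 to 3 within-group SD, VIF = 1 + gap²/4 = 2.0 to 3.25. The noncentrality is 2.844/√2.0 = 2.011 to 2.844/√3.25 = 1.578, and power is 51% to 34% even if age has no effect of its own.

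**The case against.** **Purpose.** The rule says it exists to remove confounding, and neither estradiol nor FSH is a confounder of menopausal state. A sensible analyst might leave both out. This stands as a reading of intent, but the wording is mandatory and its conditions do not test for confounding.

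**Hormones are descriptive.** Section IV.A makes forced entry less natural. The word primarily is not a bar, and no passage excludes hormones as covariates.

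**Collinearity check.** It would most likely catch a variable nearly equivalent to group. The largest power losses, 24% to 14% at an assumed R² with status of 0.80 to 0.90 (VIF 5 to 10), belong to that case and should not be taken as the expected result. A mediator with a VIF of 1.96 could easily pass, and nothing says whether the hormone or status would be dropped.

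**Body fat.** A reader might infer that adjusting for body fat simply biases the effect toward zero. The documents do not support that. BMI up to 40 is allowed and the groups differ in age, so adiposity may precede menopause as well as follow it. The only fat gain the plan quantifies is 1.0–1.5 kg over 24 weeks of leuprolide. The association in section III concerns cold-induced BAT activity, and section III also says that 11C-acetate clearance does not depend on the tissue's energy status. No slope of the primary endpoint on body fat is given, so no power figure is offered for it here.

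**Conclusion.** The point holds for ovarian hormones and FSH. Followed as written, the rule can admit the hypothesised mechanism or part of the group definition into the SA1/SA2 models and remove part or all of the effect those aims ask about. In the thermoneutral condition, where the planned power is 80%, one covariate with r = 0.7 leaves about 52% power with no mediation and 17% with half the effect mediated. Both r and the mediated share are assumptions. The figures show what the rule permits and do not predict the trial's result.

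Two stronger readings are not supported. The documents do not show that the hormones will certainly be entered, because the stated purpose and the diagnostics may keep some out. Nor would narrowing the rule secure the planned power: age is still eligible, and section IV.E concedes that the cross-sectional comparison cannot separate it from menopause.

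**What to change.** In section IV.F, Analysis strategy:

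1. State that the covariate rule applies only to variables that are neither consequences of menopausal state nor part of its definition.
2. Exclude E1, E2, progesterone and FSH from the SA1/SA2 primary models. Keep their associations with BAT as the exploratory analyses of section IV.A.
3. Classify body fat in advance. Report the estimate without it (total) and with it (fat-adjusted), each labelled, and call neither unbiased.
4. Always report the status-only model, to which the stated power applies, beside any adjusted model, including one adjusted for age.

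The cost is a few sentences and the extra labelled models, with no new data. The downside is that the status-only estimate may include confounding by age and pre-existing adiposity, and the report must say so.
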